Date: November 14, 2018

Principal Investigator: [name]

Application Number: IRB00175781

The compliance of the program

The compliance of this program will be monitored using active min and daily heart rate zone data from the wearable device (FitBit Charge 2). The weekly goals on number of day for physical activity and duration of the physical activity will be set. The number active min and duration of the heart rate in at least “Fat Burn” zone per day will be recorded for the duration of physical activity/day. The number of days the participant achieve the goals (duration and days) for physical activity will be used to measure the compliance of the program.

The descriptive information from the phase I to help inform alternative approaches to the anticipated analysis, sample size estimates for phase II, and additional key variables to be measured in phase II (intervention dose, fidelity, and additional process variables).

The program modification

Prior to phase 2, the primary investigator will discuss participants' feedback with the research teams.

The modification of exercise plan, wearable device, and phone application feature will be discussed until consensus program for each option is made.

8. Risks

Potential Risks:

The risks of participating in this study are minimal. Potential risks include

1. complications during the blood drawing for examples pain and bleeding at the drawing site.
2. complications during the sweat collection for examples rash, itching, redness and swollen.
3. minimum discomfort might occur during the wearable device (worn like a bracelet).
4. complications (e.g., fainting, injury) during the exercise program.

During the proposed study, if there is a serious adverse event, anticipated to be an uncommon occurrence, the PI will unmask treatment group assignment when necessary for the safety of the participant. The administration of the intervention may be discontinued at the participant's request or by the investigator, based on clinical judgment. Participants will be instructed to report any adverse event experienced after treatment without delay.

Adequacy of Protection against Risks: The safety of the study participants is essential. The primary investigator and research team will take all precautions to protect the participants against risks.

Protection against Risks: The principal investigator (PI) and research team plan to prevent the following risks:

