Participants will be approached and screened for the annual income below \$30,000 for families of three, average fatigue level within the past 7 days at the level of 3 or more on the 0 (no fatigue) to 10 (worse fatigue) Likert scale, the self-report perceived ability to walk for six-minute and the exertion level after the walk on a 0-10 numeric perceived exertion scale (0 = no exertion at all to 10 = maximal exertion). Eligible participants will be asked if they would like to participate and to sign the informed consent. Participants will be asked to have the research team visit their home for the initial assessment and to provide instruction on the exercise, the physical activity tracker and how to complete the questionnaire via the phone application for 4 weeks, followed by phone follow up for 7 weeks. Participants will be asked to wear the FitBit Charge 2 on the non-dominant arm and respond to the phone application daily for 12 weeks. Participants' peripheral blood will be drawn at week 1 and week 12 by a registered nurse or certified phlebotomist. We will ask the participant to have a sweat pad placed on their upper abdomen or flank for 72 hours to collect the sweat at baseline (before the program) and week 12 (at the program completion).

At the end of the program, a research team member will visit participants' home and evaluate the participants' perception and satisfaction for the program using a open ended questionnaires. Participants will be asked to complete the questionnaires. Participants' blood and sweat will be collected.

Intervention/Independent Variables

Tailored Technology-Enhance Home-based Exercise Program:

The tailored technology enhanced home-based exercise (iHBE) program: Participants in this group will receive an adjusted (based on the feedback from phase 1)12-week program with 1 assessment home visit session, 5 home visits during exercise and 7 follow up phone calls. The technologies, a wearable device and a smartphone application, will be used as a tool to monitor physical performance (heart rate, step count), provide immediate feedback, send daily reminding message through mEMA. The coded raw data without personal identification information from the wearable device will be sent to the servers where we can store it in the database alongside the mEMA data and create custom reports showing HR 30 minute before each EMA survey, showing HR and previous self-report responses before/ after each automatically triggered

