Date: November 14, 2018

Principal Investigator: [name]

Application Number: IRB00175781

EMA.

Usual Care (Waiting List) Group: The usual care waiting list group will receive educational booklets about a healthy lifestyle and cancer survivorship. Participants will be asked to wear the wearable device during the waiting period to monitor the PA (steps and heart rate). They will receive a notification to rate their daily fatigue level for 3 months. Usual Care participants will receive the iHBE after the conclusion of the study (as described above).

Variables and measurements.

The study variables will be measured as follows:

Measure	Description	Psychometrics
NINR Common Data Elements (CDEs)	23-item; measure demographic and disease information data	
PROMIS Short Form V1.0-Fatigue 6a	6-items; self-reported fatigue (frequency, duration, intensity) and the impact to physical, mental, and social activities, has five response options (1 or never to 5 or always).	Initial psychometric properties have shown an internal consistency reliability coefficient of greater than 0.80. ⁵²
PROMIS Pain Intensity – Short Form 3a V1.0.	Universal and not disease-specific instrument for pain, 3-items (worst, average, and current pain) measure from 1 (no pain) to 5 (very severe).	Conceptually validated with established reliability Test-retest values = .83 to .93. (PROMIS, 2015)
Wrist worn wearable device: FitBit Charge 2	PA (steps count and Heart rate) tracking device (wrist worn)	Intraclass Correlation Coefficients with ActivPAL are 0.81 and 0.96 respectively, $p < .01$. (Kooiman et al., 2015)
Connor-Davidson Resilience Scale	10 item self-report rating scale 0 (not true at all) to 4 (true nearly all the time)	Good internal consistency (Cronbach's alpha 0.85) and constructs validity. (Campbell-Sills & Stein, 2007)
Short form survey (SF-36)	36 item self-report instrument measure 2 domains: physical well-being and affective well-being.	Good internal consistency for every scales (Cronbach's alpha ≥ 0.70). (Busija et al., 2011)

Serum and Sweat BDNF protein levels will be measured by the enzyme-linked immunosorbent assay (ELISA). Participants' peripheral blood will be drawn during home visits, the sweat patch will be placed on the participants' upper abdomen or flank for 72 hours to collect the sweat at baseline, 12 weeks and 3 months after the program completion. The ELISA will be performed according to manufacturer's guide by one laboratory technician.

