Data Collection Schedule and Procedures:

Phase two is a pilot testing of the adjusted iHBE program effectiveness on the symptoms (fatigue and pain) affective well-being, resilience and BDNF level. A randomized usual care (waiting list) trial phase will be used. The study flyers will be posted at the home health care agencies, Johns Hopkins Comprehensive Cancer Center and Johns Hopkins Hospital. Eligible participants will be contacted by the principal investigator or research assistant who will explain the purpose of the study and requirements, and provided the study information and consent form. After providing the signed consent form, participants will complete the baseline assessment including the questionnaire, physical function (FTSST and 6MWT)

Date: November 14, 2018

Principal Investigator: [name]

Application Number: IRB00175781

and blood samples. A pre-installed application smartphone and a wrist-worn wearable device (FitBit Charge 2) will be loaned to the participants. The online account specific to the participant will be assigned using code. No personal information will be stored separately. Participants will be asked to wear the FitBit Charge 2 on the non-dominant arm and respond to the mEMA application to monitor their free-living PA level for 7 days then randomly assigned to the experiment and usual care waiting list group. Participants in the iHBE group will receive one assessment home visit, 5 home visits and 7 follow up phone calls during the iHBE program. Then a home follows up visit at 6 month. The usual care (waiting list) group will receive educational booklets about a healthy lifestyle. They will be asked to continue to wear the wearable device to monitor PA for 3 months. Participants will then receive the iHBE program after the conclusion of the 12-week program.

5. Inclusion/Exclusion Criteria

Inclusion criteria are (1) participants diagnosed with solid tumor cancer who have completed cancer treatment at least 6 months; (2) diagnosed with diabetes and/or hypertension for at least a year; (3) aged 21 years or older, (4) have an annual household incomes of below \$30,000 for families of three, (5) the average fatigue level within the past 7 days at the level of 3 or more on the 0 (no fatigue) to 10 (worse fatigue) Likert scale and (6) give informed consent.

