Exclusion criteria are those (1) currently undergoing treatment for cancer; (2) have an active infection (e.g., fever, localized redness, swelling, sinus congestion); and/or (3) diagnosed with a psychological disorder (e.g., suicidal or homicidal tendencies, extreme anxiety or depression).

6. Drugs/Substances/Devices

None

7. Study Statistics

Phase 2 Data analysis

To test **Hypothesis 2 (Aim 2)** examining the effectiveness of iHBE program on fatigue, pain, well-being, resilience and BDNF levels, generalized estimating equations (GEE) will be used. The models will include time as a within-subject fixed effect (baseline, 3 months, 6 months), group (intervention vs usual care) as a fixed-effect between-subject factor and the group by time interaction. Baseline age, race gender, and BMI will be included as covariates. A significant group by time interaction would signify that the change over time in the outcomes differed for the intervention and usual care groups. GEE was selected because it uses all available data and does not require complete data across time for a participant to be included in the analyses. Correlation will be used to test the relationship between the changes in serum and sweat BDNF levels (**Aim 3**). Change from baseline to 3 months and change from baseline to 6 months will be computed for serum BDNF and separately for sweat BDNF. The correlation between the change scores measured by the different modes will be estimated at each time point

8. Risks: Same as phase 1

9. Benefits: Same as phase 1

10. Payment and Remuneration

Date: November 14, 2018

Principal Investigator: [name]

Application Number: IRB00175781

Phase 2 (Aim 2 and 3) - The participants in both the intervention group and the control group will each receive a total of \$80 (\$20 at the start of the intervention, \$30 at the end of the intervention and \$30 at 6 months)

11. Costs

There will be no cost for participants to participate in this study.

12. Data Safety Monitoring Plan

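### The adverse-event instruction does not clearly cover the exercise period or usual care, and staff contact is unequal by arm, so Phase 2 events can be missed and counts by arm would not be comparable

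*Combined protocol and SAP*

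**What the plan says.** All references are to the combined protocol and SAP.

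- **Reporting rule.** Section 8 (Risks, Phase 1) gives the only instruction to participants about adverse events: "Participants will be instructed to report any adverse event experienced after treatment without delay".
- **Named risks.** The same section lists "complications (e.g., fainting, injury) during the exercise program". Its later part on protection against risks adds falls, and commits staff to watching exercise at the first four weekly home visits.
- **Carry-over.** The whole Phase 2 text on risks is "8. Risks: Same as phase 1".
- **iHBE contacts.** Phase 2, Intervention/Independent Variables describes a 12-week "program with 1 assessment home visit session, 5 home visits during exercise and 7 follow up phone calls". Phase 2, Data Collection Schedule and Procedures repeats the count: "Participants in the iHBE group will receive one assessment home visit, 5 home visits and 7 follow up phone calls during the iHBE program". The Phase 2 recruitment text says the home instruction runs "for 4 weeks, followed by phone follow up for 7 weeks".
- **Usual-care contacts.** Phase 2, Usual Care (Waiting List) Group: "The usual care waiting list group will receive educational booklets about a healthy lifestyle and cancer survivorship". They wear the device, and "They will receive a notification to rate their daily fatigue level for 3 months". No visit or call is listed for this arm between baseline and week 12.
- **Oversight.** Section 12 (Data Safety Monitoring Plan) gives the investigator review duties and monthly reports that include a summary of adverse events, and has the Safety Monitoring Committee (SMC) meet annually.

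**The concern.** The intervention is a continuous programme of 4 weeks in Phase 1 and 12 weeks in Phase 2, done mostly at home without staff present. A rule keyed to the time *after treatment* points, on its face, away from the weeks in which the named complications would occur. The randomised phase takes over a paragraph written for a single-arm open-label phase, so it does not say what the rule means for people who have not yet been offered the programme.

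The second problem is opportunity. Where events are not asked about on a fixed schedule, they tend to surface when someone talks to a member of staff. One arm has many such occasions and the other has none listed. Any tabulation of events by arm would then mix true differences with differences in how often people could mention something. That matters for the investigator's and SMC's view of safety, and for a pilot meant to inform later trials.

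**Working it through.** **Step 1. The reporting window.** There are two readings.

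- *After treatment has ended.* The programme weeks fall outside the window, although section 8 places its exercise complications within the programme.
- *After treatment has started.* The programme weeks are covered for iHBE. Usual care does not receive the programme before week 12, so the start of its window is undefined.

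Neither reading gives one window that is clear for both arms.

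**Step 2. Scheduled staff contacts in Phase 2.** The plan prints 1 assessment visit, 5 home visits and 7 calls, but no total.

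- All counted: 1 + 5 + 7 = 13.
- Assessment visit treated as baseline: 5 + 7 = 12.
- Fifth home visit treated as the week-12 visit: 1 + 4 + 7 = 12. This is an inference: 4 weeks of home instruction plus 7 weeks of calls cover 4 + 7 = 11 weeks, which leaves week 12.
- Both set aside: 4 + 7 = 11.

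Usual care has 0 listed between baseline and week 12. Both arms are measured at baseline, 12 weeks and 6 months. The like-for-like contrast is therefore 11 to 13 against none listed.

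**Step 3. How much exercise staff would see.** Table 1 (Phase 1) gives 15 to 20 minutes of practice at each weekly visit. The Phase 1 feasibility example uses a goal of 3 days a week. If that goal applied and each visit's practice counted as one session (both assumptions):

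- Phase 1: 4 of 3 × 4 = 12 sessions observed, or 33%.
- Phase 2, four visits: 4 of 3 × 12 = 36 sessions, or 11%.
- Phase 2, if the fifth visit is also observed: 5 of 36, or 14%.

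Most sessions are unobserved in both phases, including those in weeks 1 to 4.

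**Step 4. What is asked.** No section gives an adverse-event question, form or recall period for either arm. The Phase 1 data collection table has no row for events. The usual-care app prompt concerns fatigue. Section 12 governs the review of what has been collected; it does not add collection.

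**Step 5. What this could do to counts.** Expected recorded events in an arm = n × p × c, where n = 25 per group (Sample size justification), p is the true event risk and c is the share of events captured. The plan gives neither p nor c. With p = 0.20 in both arms, assumed for illustration:

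| c, iHBE | c, usual care | Recorded events | Ratio |
|---|---|---|---|
| 0.90 | 0.90 | 4.5 v 4.5 | 1.0 |
| 0.90 | 0.60 | 4.5 v 3.0 | 1.5 |
| 0.90 | 0.30 | 4.5 v 1.5 | 3.0 |
| 0.60 | 0.90 | 3.0 v 4.5 | 0.67 |

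The last row covers the case in which iHBE participants take the literal window seriously and hold back events during exercise. The table shows only that the ratio follows c and that either direction is possible. It estimates nothing about this trial.

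**The case against.** The strongest reply is that this is loose wording in a plan that otherwise intends to capture everything.

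- The instruction to report promptly fits *after treatment starts* better than a wait until the programme ends. The neighbouring sentence on serious events covers the whole study, and section 12 sets no post-treatment limit.
- The Randomization paragraph calls both groups treatment arms, so usual care is arguably within the rule.
- In the Phase 1 programme, staff discuss exercise problems at weekly visits, participants log heart rate, fatigue and pain after sessions, and a checklist is completed at each home visit.
- Section 7 plans no comparison of adverse events between arms, and no aim estimates a harm rate.
- The consent form, which I have not seen, may say more.

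Much of this stands, and it rules out several stronger inferences. A reader might conclude that the rule excludes exercise events or cannot apply to usual care; each is one reading, and *unclear* is as far as the text goes. A reader might set 13 contacts against 0, but the 13 may include a baseline and a week-12 visit while the 0 excludes both. A reader might take the weekly visits to have covered all exercise in Phase 1; they covered short practice periods. A reader might expect a particular inflation of the iHBE count, but no capture rate in the documents supports one.

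The core is not answered. None of the items above is an adverse-event question. Those that involve staff visits or exercise sessions exist only where the programme is delivered, so in Phase 2 they add to the imbalance.

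**Conclusion.** The point holds in a limited form. The only participant-level instruction either omits the exercise period or is undefined for usual care before week 12. Scheduled staff contact is 11 to 13 in iHBE against none listed in usual care, and no common question offsets the difference. Events in unsupervised sessions can be missed, and event counts by arm in the monthly or SMC summaries, or in any later report, would not be comparable.

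The efficacy analysis is unaffected and no planned test is invalidated. The size and direction of the bias are unknown. The imbalance is one of opportunity to report, since the iHBE contacts are not described as asking about events either. The conclusion assumes that Phase 2 keeps the contact schedule as printed and that no separate event form exists outside these documents.

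One conflict bears on the later period. The Usual Care section gives that arm iHBE after the study concludes, while the Phase 2 Data Collection section gives it after the 12-week programme. Which applies decides whether usual-care events between week 12 and 6 months could arise during the exercise programme. The two passages must be reconciled.

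**What to change.** 1. Reword the sentence in section 8 so that participants in both arms report any adverse event from consent to the 6-month visit, including during exercise. State it in Phase 2 in its own right rather than by reference.
2. Add one short, identical item (any fall, faint or near-faint, injury, skin reaction or unplanned care) at the same interval in both arms, through the app prompts already planned for about 3 months. Repeat it at the 12-week and 6-month assessments.
3. Use these equally timed answers for any by-arm summary up to week 12. Report events first learned at iHBE visits or calls separately.
4. Reconcile the two statements on when usual care receives iHBE before making any by-arm summary after week 12.

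The cost is slight participant burden, time for existing staff to review the app answers, and probably a higher recorded event rate. No new visits or procedures are needed.

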Phase 2: With an alpha level of .05, the statistical power of 0.80, and 25 participants per group, we will be able to detect significant differences of moderate to large effect sizes of 0.65 when comparing change across baseline, 3-months, and 6-months between the two groups. With an attrition rate of 12% (22 participants per group), the detectable effect size increases to 0.69. Since this is a pilot study and not powered to detect small to moderate effect sizes, we will pay close attention to the effect size, rather than statistical significance. These effect size estimates will be used to inform future research trials.

Date: November 14, 2018

Principal Investigator: [name]

Application Number: IRB00175781

Randomization: Eligible participants will be randomized in a 1:1 allocation ratio to one of the two treatment arms. The electronic Research Electronic Data Capture (REDCap), a randomization application will be used to randomly assigned the participants to the groups

Data Collection Schedule and Procedures. Upon receiving approval from the Johns Hopkins University Institutional Review Board, the study flyer will be posted and distributed at the home health care agencies in Baltimore, Maryland, Johns Hopkins Comprehensive Cancer Center and Johns Hopkins Hospital.

Recruitment, Informed Consent, and Confidentiality. Recruitment methods for this study include (1) distributing and posting flyers, with a tear-off phone number to speak with the principal investigator (PI) as necessary, posted at the hospital (2) face-to-face recruitment for potential participants during cancer support group meetings; and (3) word-of-mouth. Potential participants will receive a verbal explanation by phone or face to face meeting in terms suited to their comprehension of the purpose, procedures, and potential risks of the study. During the screening for eligibility process, an oncologist will be available for consultation. The oncologist will be notified and consulted for the appropriateness of the exercise for participants who self-report having co-morbidities. The participants and family or legal guardian will have an opportunity to carefully review the consent form and ask questions regarding this study prior to signing. Participants will be encouraged to consult with their primary doctor if any concern or an additional question. Participants will be informed that they may withdraw from the study at any time without prejudice to themselves.

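### Are the Phase 2 detectable effects of 0.65 and 0.69 unsupported because the within-person correlation behind them is not stated?

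*Combined protocol and SAP*

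**What the plan says.** The Phase 2 sample size justification starts from "With an alpha level of .05, the statistical power of 0.80, and 25 participants per group" and concludes that "we will be able to detect significant differences of moderate to large effect sizes of 0.65 when comparing change across baseline, 3-months, and 6-months". It then allows for dropout: "With an attrition rate of 12% (22 participants per group), the detectable effect size increases to 0.69". It goes on to say that this is a pilot without power for small to moderate effects, and that attention will go to effect size rather than to significance.

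Phase 2, section 7 (Study Statistics) plans generalized estimating equations (GEE) with group, time at three levels (baseline, 3 and 6 months) and their interaction, adjusted for age, race, gender and BMI. The key test is described this way: "A significant group by time interaction would signify that the change over time in the outcomes differed for the intervention and usual care groups". With two groups and three time points, that test has 2 degrees of freedom.

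The documents give no within-person correlation, correlation structure, scaling SD, sidedness or pattern of effects for the power statement. The nearest figure is in the Phase 2 measures table, for the pain scale only: "established reliability Test-retest values = .83 to .93". That describes the reliability of the scale, is not tied to a 3- or 6-month interval, and is not linked to the sample size.

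**The concern.** For a comparison of change over repeated visits, the detectable effect depends strongly on how well a person's scores correlate between visits, and on whether the effect is counted in SDs of a single visit or SDs of change. Without these, a reader cannot reproduce 0.65 and 0.69. The obvious first attempt, a two-group comparison at one visit, gives clearly larger values. The same figure is also applied to five outcomes (fatigue, pain, affective well-being, resilience and BDNF), whose correlations over time may well differ.

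If the true correlations were low, the trial would have less than the claimed 80% power, and a non-significant interaction could be read too confidently as absence of effect.

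**Working it through.** **Inputs.** From the sample size justification: alpha 0.05, power 0.80, n = 25 or 22 per group. Assumed here, because not stated: two-sided test, complete data, equal correlation ρ between visits, effect d in single-visit SDs, and the same d at 3 and 6 months.

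**1. Stated inputs alone.** For a two-sample comparison at one visit, the noncentrality is d√(n/2).
- Normal approximation, two-sided: d = (1.960 + 0.842)√(2/n) = 0.792 (n = 25) and 0.845 (n = 22).
- Noncentral t, two-sided: 0.809 and 0.865. One-sided: 0.713 and 0.762.

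None of these gives 0.65 and 0.69, so a further assumption was used.

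**2. Attrition step.** 25 × 0.88 = 22, and 0.65 × √(25/22) = 0.693. The two stated figures agree with each other.

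**3. The planned 2-df interaction.** With group differences (0, d, d), the noncentrality is λ = n d² / [3(1 − ρ)]. For 80% power, λ = 9.942 with F(2, 96) and 9.987 with F(2, 84). Solving for ρ:
- n = 25: ρ = 1 − 25 × 0.65² / (3 × 9.942) = 1 − 10.5625/29.826 = 0.646.
- n = 22: ρ = 1 − 22 × 0.69² / (3 × 9.987) = 1 − 10.474/29.961 = 0.650.

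Put the other way, at ρ = 0.65 the detectable effect is √(3 × 9.942 × 0.35/25) = 0.646 and √(3 × 9.987 × 0.35/22) = 0.690. Both round to the plan's figures. A Wald chi-square reference moves the required ρ to 0.635 and 0.638; a multivariate F moves it to 0.657 and 0.663.

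**4. Other routes to the same pair.** Each multiplies a two-sided result from step 1 by the factor shown.

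| Calculation | Factor | ρ | n = 25 | n = 22 |
|---|---|---|---|---|
| Mean of follow-ups minus baseline (normal) | √[1.5(1 − ρ)] | 0.55 | 0.651 | 0.694 |
| Group difference averaged over three visits (normal) | √[(1 + 2ρ)/3] | 0.5 | 0.647 | 0.690 |
| One follow-up, adjusted for baseline (t) | √(1 − ρ²) | 0.6 | 0.647 | 0.692 |

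So 0.65 cannot be taken as the correlation the sponsor assumed. It is what one particular test, scale and effect pattern would need.

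**5. Sensitivity of the planned test** (F, n = 25/n = 22).

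| ρ | Detectable d, equal effects | Power at 0.65/0.69 | Detectable d, 6-month effect half the 3-month | Power at 0.65/0.69 |
|---|---|---|---|---|
| 0.3 | 0.91/0.98 | about 49% | 1.06/1.13 | about 38% |
| 0.5 | 0.77/0.83 | about 64% | 0.89/0.95 | about 51% |
| 0.7 | 0.60/0.64 | about 86% | 0.69/0.74 | 74–75% |
| 0.8 | 0.49/0.52 | about 97% | 0.56/0.60 | about 90% |

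With the halved effect, 80% power needs ρ = 0.734/0.738. With first-order autoregressive correlation and equal effects, the adjacent-visit correlation must be 0.729/0.733. If the effect is scaled by the SD of change, divide d by √[2(1 − ρ)]; with equal effects the planned test then detects 0.772/0.825 whatever ρ is, so 0.65 is not reached on that scale. At ρ = 0.83, the low end of the pain reliability range, the test detects 0.45/0.48 single-visit SD, and the plan's figures would be conservative.

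**The case for a change.** The best case for asking for a change has three parts.

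First, Study Statistics still interprets a significant interaction, so power is not irrelevant, and one undocumented correlation is made to serve five outcomes. This stands as a description: for any one outcome the true power is not known from the documents, and step 5 shows how wide the range is. It does not show that power is too low, because the departure can go either way.

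Second, the effect sizes are meant to inform later trials, and an effect without a stated SD is hard to carry forward. At ρ = 0.65, an effect of 0.65 single-visit SD equals 0.65/√0.70 = 0.78 SD of change. The arithmetic is right, but a later trial will use effects estimated from this trial's data, with SDs and correlations that the analysts can compute and report. The planning value does not enter that step.

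Third, Phase 1 is meant to help: "The descriptive information from the phase I to help inform alternative approaches to the anticipated analysis, sample size estimates for phase II". Eight participants over 4 weeks cannot settle a correlation. An observed 0.65 has Fisher z = 0.775 with standard error 1/√5 = 0.447, which gives a 95% interval of −0.10 to 0.93. That is correct, and Phase 1 should not be relied on for this number. The text does, however, present Phase 2 planning as provisional: Phase 1, section 4 says Phase 2 will be submitted separately.

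The single-visit benchmark of 0.81 and 0.86 is weaker evidence than it looks. The plan names a comparison across three time points, and a smaller detectable effect than a single-visit t-test is what one expects when repeated scores are correlated strongly enough.

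**Conclusion.** No change to the plan follows. The sample size section leaves out the test, effect scale, sidedness, correlation and effect pattern behind its figures, but 0.65 and 0.69 are consistent with each other and can be reached under ordinary assumptions. One of these is the planned group-by-time test at a correlation of about 0.65, given equal correlations, equal effects at 3 and 6 months, single-visit SDs and complete data. The figures are under-specified, not shown to be miscalculated.

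The omission makes power at the stated effects uncertain, from about 49% to 97% for correlations of 0.3 to 0.8 with equal effects. Nothing in the trial turns on that. The section starts from 50 participants and works out the effect, rather than deriving the number from a target; no go/no-go rule uses 0.65 or 0.69; the GEE analysis is the same at any correlation; and the plan already puts effect size ahead of significance. Writing down the assumption would help a reader reproduce the figures, but would alter neither the number recruited, nor the analysis, nor what can be concluded.
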